- 8 Including at **screening**: sodium, potassium, chloride, CO2, calcium, magnesium, phosphorus, blood urea nitrogen (BUN), creatinine, glucose, albumin, total protein, alkaline phosphatase, total bilirubin, AST (SGOT), ALT (SGPT), lactate dehydrogenase (LDH), and uric acid, creatine kinase (CK); at **baseline and on study assessments** (30-mL) include all screening studies as well as: drug levels if pertinent (tacrolimus, cyclosporine, sirolimus), immunoglobulin levels, CMV PCR at least every other week the first 12 weeks, then every 4 weeks until 24 weeks. CMV PCR will not be performed at remote visits unless clinically indicated. Note: Baseline studies performed within the appropriate timeframe at screening need not be repeated. (See section [2.4](#))
- 9 Includes primary and secondary measurement of response, performance scale, global rating ([Appendix D](#), [Appendix E](#), [Appendix F](#), [Appendix G](#), [Appendix I](#)). Note: The response assessment in [Appendix H](#) is not performed at baseline.
- 10 Skin and oral biopsies, saliva and microbiome swab collection will be performed at baseline and after 6 months of treatment, with intent to sample as close to the same area as possible. At baseline, the saliva and oral microbiome swabs will be collected at the time of the oral biopsy, if performed.

- 11 Blood (48 mL in 6 CPT tubes) for immunologic studies will be drawn prior to first drug at all timepoints. PD baseline assay will be performed using some of the blood for immunologic studies. PD studies at the peak blood level of baricitinib will be performed on a 6ml (green topped heparin) tube collected at 2 hours post drug at Cycle 1 Day 1. PD studies will be repeated at any increase in drug dose.

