5.1.2 Immunologic Analyses Using Plasma and PBMCs

1. **Blood:** Blood will be collected, and PBMC and plasma will be cryopreserved for later batch analyses of markers relevant to cGVHD activity. Cellular markers of active cGVHD have been proposed, although not verified at multiple institutions or validated in prospective trials²⁷. Heparinized plasma will be assayed for potential markers of cGVHD activity (including but not limited to BAFF, IFN-induced chemokines). Pharmacodynamic of baricitinib (inhibition of cytokine-induced STAT phosphorylation) will be assayed prior to drug administration and 2 hours post administration on the first day of cycle 1 and at any later increase in drug dosage. Monocyte transcriptome assessments of IFN-inducible genes should be noted to be an experimental endpoint with potential relevance to cGVHD pathogenesis. PBMC will be cryopreserved for subsequent flow cytometry of cell populations and sorting of monocytes for transcriptional analysis of genes upregulated in active cGVHD. The primary collection of blood for these analyses of baricitinib effect on cGVHD will be collected prior to dose and 2 hours after dose at the following timepoints: baseline, at the time of any increase in dose level. Each aliquot contains 10×10^6 cells—with no more than cells in a single vial. All samples collected will be cryopreserved and frozen for future analyses as detailed in Section 5.2.1.
2. **Plasma** will be assayed for BAFF, CXCL9/CXCL10, IL-6, TNF α , and other IFN-induced chemokines. Take one 1 mL aliquot of plasma from each of the CPTs, without disturbing the cell interface, and place into standard cryovials. Barcode as buffy plasma and store at -80°C. All samples collected will be cryopreserved and frozen for future analyses as detailed in Section 5.2.1.
 1. Additionally, ELISA assays may include but not be limited to the following proposed biomarkers of cGVHD: CXCL9, MMP3, DKK3, ST2, CD163
 2. Additional or alternative plasma factors will be considered based upon relevant cGVHD biomarkers identified by the end of biospecimen accrual.
3. **Monocyte transcriptome:** Monocytes will be sorted from PBMC for Nanostring evaluation of the monocyte transcriptome. This would be done on cryopreserved cells at the end of the study. Monocytes circulate throughout the body, are responsive to a variety of cytokines in tissues affected by cGVHD and may therefore serve as a reporter for changes in cGVHD-affected tissues.

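### The pre-dose and 2-hour pharmacodynamic samples are specified in different tube types, so any tube or handling effect would be confounded with baricitinib effect

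*Combined protocol and SAP*

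**What the plan says.** Three statements in footnote 11 of the Study Calendar (section 3.7) set the PD specimens.

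- The immunology blood: "Blood (48 mL in 6 CPT tubes) for immunologic studies will be drawn prior to first drug at all timepoints".
- The PD baseline: "PD baseline assay will be performed using some of the blood for immunologic studies".
- The PD sample at peak drug level, on Cycle 1 Day 1: "will be performed on a 6ml (green topped heparin) tube collected at 2 hours post drug".

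For later dose levels the footnote adds "PD studies will be repeated at any increase in drug dose", without restating the tubes.

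Section 5.1.2 defines what is compared. Inhibition of cytokine-induced STAT phosphorylation "will be assayed prior to drug administration and 2 hours post administration on the first day of cycle 1", and again at any later dose increase. That section names no tube for this assay. Section 1.1.2 lists the description of pharmacokinetics and pharmacodynamics as a secondary objective.

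**The concern.** A pre/post PD measure uses each patient as their own control, so the two specimens should differ only in time since dose. Here they also differ in collection tube, and the two differences coincide: CPT is always before, heparin always after. The study is single-arm, so no undosed group given the same pair of tubes could show what the tube change does by itself.

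The PD result has some weight. Section 1.2.2 says that STAT phosphorylation has not been studied in cGVHD, in animals or in patients, and that this trial will address it. The documents therefore offer no earlier cGVHD value against which a distorted estimate would stand out.

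The plan controls this kind of difference elsewhere. Footnote 12 uses one tube type (EDTA) for the PK samples, footnote 10 aims repeat biopsies at the same area, and section 6.3.2 requires the same assessment methods at baseline and on study.

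**Working it through.** The plan states no figure that depends on the tubes, so there is none to reproduce. The check sets the text side by side and then illustrates the possible size.

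**Specimens on Cycle 1 Day 1**

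| | Pre-dose | 2 hours |
|---|---|---|
| Tube | CPT (part of 48 mL in 6 tubes) | separate heparin tube, 6 mL |
| Anticoagulant | not stated for the CPTs | heparin |
| PD processing | not stated for this assay | not stated for this assay |
| Source | footnote 11 | footnote 11 |

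Tube type and time point are fully aligned in the written default.

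**Illustration of size**

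Inputs:
- *I*, true inhibition: assumed values. The only figure in the documents is a 70% reduction at 10 mg (section 1.2.3), a dose not used in this trial.
- *k*, the ratio of heparin-tube to CPT signal for the same blood: not in the documents; assumed range 0.80 to 1.25.

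Formulas:
- apparent inhibition = 1 − (1 − *I*) × *k*
- bias = apparent − true = (1 − *I*) × (1 − *k*)

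For *I* = 30%:
- *k* = 0.80: 1 − 0.70 × 0.80 = 44%, a bias of +14 points.
- *k* = 1.25: 1 − 0.70 × 1.25 = 12.5%, a bias of −17.5 points.

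| True inhibition | k = 0.80 | k = 0.90 | k = 1.00 | k = 1.10 | k = 1.25 |
|---|---|---|---|---|---|
| 70% | 76% | 73% | 70% | 67% | 62.5% |
| 50% | 60% | 55% | 50% | 45% | 37.5% |
| 30% | 44% | 37% | 30% | 23% | 12.5% |
| 0% | 20% | 10% | 0% | −10% | −25% |

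Two things follow. The bias formula contains no sample size: averaging over patients reduces random error and leaves this term where it is. And for a given *k*, the shift is larger when true inhibition is smaller. With matched tubes and processing, *k* = 1 and the apparent value equals the true one.

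**The case against.** A reader might infer that the STAT-inhibition estimate is in fact biased in every patient. The documents do not support that, for these reasons.

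- **No effect is shown.** Nothing in the text gives a tube effect other than zero, and *k* = 1 is possible.
- **The anticoagulant may be the same.** Section 5.1.2 says "Heparinized plasma will be assayed for potential markers of cGVHD activity", and for the plasma aliquots it says "Take one 1 mL aliquot of plasma from each of the CPTs, without disturbing the cell interface". Together these suggest, without proving, that the CPTs also hold heparin.
- **Different processing is not stated.** Section 5.1.2 describes the pre-dose and 2-hour research blood together and says that all samples are cryopreserved. Normalising to an unstimulated aliquot of the same tube, if done, could cancel part of any effect.
- **It need not apply to every pair.** Section 5.1 lets tubes be substituted with permission, and footnote 11 names the heparin tube only for Cycle 1 Day 1.
- **The text is incomplete.** A part between sections 5.1.3 and 5.2 was not available, so a matching rule there cannot be ruled out.

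A reader might also scale the 70% figure down to the trial doses. A one-site model with full maximal inhibition and exposure linear in dose gives 0.70/0.30 = 2.333 at 10 mg, hence 0.467/1.467 = 31.8% at 2 mg. A tube effect of 10 to 20 percentage points would then be 31% to 63% of the 2 mg signal. That treats an assumed effect as points of inhibition. If it is a 10 to 20% loss of signal, the shift is 0.682 × 10 to 20% = 6.8 to 13.6 points, or 21% to 43% of 31.8%. The model and the tube effect are both assumptions, so neither range is a finding.

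Finally, the objective is descriptive. Section 10 sets no PD test or decision rule, and dose changes follow response and toxicity.

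These points remove any claim of a demonstrated bias. They do not remove the mismatch, which the plan states in so many words. A shared anticoagulant would not by itself make the tubes equivalent, since the CPTs separate cells in the tube and no handling is given for the heparin tube.

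**Conclusion.** The point holds in conditional form. As written, the Cycle 1 Day 1 PD pair uses CPT blood before dosing and heparin-tube blood at 2 hours, so a tube or handling difference, if there is one, is confounded with baricitinib effect.

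Its actual size cannot be computed from the documents. Under the assumed ratio of 0.80 to 1.25, a true 30% would read anywhere from 44% down to 12.5%, in an unknown direction, and would be unbiased at a ratio of 1.

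The consequence is confined to the secondary PD description. The co-primary safety and efficacy endpoints, and the design for 21 evaluable patients, are unaffected. This is a cheap improvement.

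**What to change.** In footnote 11 and section 5.1.2, require the pre-dose and 2-hour PD samples to be collected in the same tube type and to be processed and assayed identically, on Cycle 1 Day 1 and at each dose increase. The simplest route is to add a 6 mL heparin tube to the existing pre-dose draw and leave the CPT collection as it is for the other immunologic studies. State the PD processing and the CPT anticoagulant in the same place.

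The cost is 6 mL more blood per PD day, at a draw already scheduled, and a sentence in each section. The drawback is that new pairs would not be directly comparable with pairs already collected. Assaying both pre-dose tubes in some patients would estimate the heparin/CPT ratio and allow the two sets to be bridged.

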3.8 COST AND COMPENSATION

3.8.1 Costs

NIH does not bill health insurance companies or participants for any research or related clinical care that participants receive at the NIH Clinical Center. If some tests and procedures are performed outside the NIH Clinical Center, participants may have to pay for these costs if they are not covered by an insurance company. Medicines that are not part of the study treatment will not be provided or paid for by the NIH Clinical Center.

3.8.2 Compensation

Participants will not be compensated on this study.

3.8.3 Reimbursement

The NCI will cover the costs of some expenses associated with protocol participation. Some of these costs may be paid directly by the NIH and some may be reimbursed to the participant/guardian as appropriate. The amount and form of these payments are determined by the NCI Travel and Lodging Reimbursement Policy.

3.9 CRITERIA FOR REMOVAL FROM PROTOCOL THERAPY AND OFF STUDY CRITERIA

Prior to removal from study, effort must be made to have all subjects complete a safety visit approximately 30 days following the last dose of study therapy.

3.9.1 Criteria for removal from protocol therapy

- Completion of 12-month course of protocol therapy
- Progressive cGVHD or malignancy requiring new line of systemic therapy
- Participant requests to be withdrawn from active therapy
- Positive pregnancy test
- Unacceptable toxicity as defined in Sections [3.1.1](#) and [3.3](#)
- Dose interruption longer than 28 days
- Investigator discretion

The PI is to be notified of all discontinuations from study drug. The reason for dose modification/discontinuation should be recorded in the CRF and in the patient's medical records.

3.9.2 Off-Study Criteria

- Completed 2 year follow up period
- Subject withdrawal from follow-up period
- Patient lost to follow-up
- Investigator discretion
- Death

3.9.3 Lost to Follow-up

A participant will be considered lost to follow-up if he or she fails to return for 3 scheduled visits and is unable to be contacted by the study site staff.

The following actions must be taken if a participant fails to return to the clinic for a required study visit:

- The site will attempt to contact the participant and reschedule the missed visit within one month and counsel the participant on the importance of maintaining the assigned visit schedule and ascertain if the participant wishes to and/or should continue in the study.
- Before a participant is deemed lost to follow-up, the investigator or designee will make every effort to regain contact with the participant (where possible, 3 telephone calls and, if necessary, an IRB approved certified letter to the participant's last known mailing address or local equivalent methods). These contact attempts should be documented in the participant's medical record or study file.
- Should the participant continue to be unreachable, he or she will be considered to have withdrawn from the study with a primary reason of lost to follow-up.

4 CONCOMITANT MEDICATIONS/MEASURES

All medications (prescription and non-prescription), treatments and therapies taken throughout the study must be recorded on the appropriate page of the CRF. Patients will be advised to contact the study team before starting any new medications.

4.1 CONCOMITANT CORTICOSTEROID THERAPY AND TAPERING GUIDELINE

During the study, patients may remain on corticosteroids with intent to taper. A steroid taper will be allowed to begin earliest at 4 weeks after starting on the Phase 1b continuation phase or Phase 2 study, with a 10% (of starting dose) decrease per week. The study allows maximum two total pulses of steroids with subsequent rapid taper for cGVHD flares associated with the study drug initiation and/or one time later for any flares or worsening of cGVHD symptoms during steroid or other immunosuppression taper or treatment interruptions. Typical corticosteroid pulse is defined as up to 2 mg/kg/day prednisone or equivalent tapered to the pre-pulse baseline within 3 weeks. Steroid pulses require the PI's approval. Administration steroid pulses will be carefully recorded in the protocol case report forms.

4.2 OTHER TREATMENTS FOR cGVHD

Patients who are taking concomitant systemic agents for control of cGVHD, such as calcineurin inhibitors (e.g., tacrolimus or cyclosporine) or other immunosuppressants (e.g., mycophenolate or sirolimus) must be on a stable or tapering dose in the preceding 4 weeks with an intent to stop if possible after corticosteroids are at stable or supplementation doses (maximum 7.5 mg prednisone/day) or discontinued. Patient should not receive any investigational drugs or initiate any systemic therapy for cGVHD once started on baricitinib. Patients should not be undergoing extracorporeal photopheresis (ECP) concomitantly with study drug.

4.3 OTHER ALLOWED CONCOMITANT THERAPY

Ancillary therapy and supportive care considered necessary for the patient's wellbeing may be administered at the discretion of the PI and will follow the NIH Blood and Marrow Transplant Consortium guidelines for supportive care:

<http://intranet.cc.nih.gov/bmt/clinicalcare/guidelines.shtml>. Any ancillary or supportive care which may have some effect on efficacy analysis including topical cGVHD treatments will be carefully recorded in the CRF.

4.4 PROHIBITED CONCOMITANT THERAPY

Given risk of concurrent NSAID use to decrease potential of the kidney to respond to hemodynamic changes and subsequent renal dysfunction, NSAID use will not be allowed during the course of baricitinib treatment.

Baricitinib does not have significant impact on CYP enzymes, and thus the potential to cause clinically significant interaction via CYP are low. There is no specific contraindication on this study for CYP-metabolized agents.

In addition, radiation therapy, cancer chemotherapy, biologic or immunotherapy is prohibited during participation in this study. Concomitant use of other investigational agents is not permitted while persons are receiving study drug.

5 CORRELATIVE STUDIES FOR RESEARCH

5.1 BIOSPECIMEN COLLECTION

Please note that tubes and media may be substituted based on availability with the permission of the PI or laboratory investigator.

5.1.1 Skin and oral biopsy, saliva collection, oral microbiome swabs

Skin and oral research biopsies will be performed before treatment and after 6 months of baricitinib treatment (with intent to sample as close to the same area as possible). Immunohistochemistry methods will be applied to look for T-cell infiltrates, and IFN-induced factors in the oral mucosa and erythematous skin. The advantage of histology is the greater amount of information on cell populations and functional changes in situ of the disease. These biopsies will be obtained by one of the study investigators and processed, stored and analyzed at the Blood Processing Core ([name]). A biopsy sample will be also sent to the NCI pathology laboratory. Patients will have an option to decline any of these research biopsies. Biopsy samples collected on the 04-C-0281 cGVHD natural history study can be also used for these studies if obtained in the timeframe as part of the screening evaluations for this study.

Whole saliva and oral swabs of the buccal mucosa, tongue and gingiva will be collected at the same time that the buccal mucosal biopsies are performed to evaluate the salivary proteome, microbiome and cytokine profile at baseline and after 6 months of baricitinib treatment. The samples may be analyzed using a variety of methods including immunohistochemistry, microscopy, gene expression profiling, microbial sequencing, and protein-based assays in order to assess oral tissues for immune changes and for local specific markers of response or lack thereof to baricitinib therapy.

5.1.2 Immunologic Analyses Using Plasma and PBMCs

1. **Blood:** Blood will be collected, and PBMC and plasma will be cryopreserved for later batch analyses of markers relevant to cGVHD activity. Cellular markers of active cGVHD have been proposed, although not verified at multiple institutions or validated in prospective trials²⁷. Heparinized plasma will be assayed for potential markers of cGVHD activity (including but not limited to BAFF, IFN-induced chemokines). Pharmacodynamic of baricitinib (inhibition of cytokine-induced STAT phosphorylation) will be assayed prior to drug administration and 2 hours post administration on the first day of cycle 1 and at any later increase in drug dosage. Monocyte transcriptome assessments of IFN-inducible genes should be noted to be an experimental endpoint with potential relevance to cGVHD pathogenesis. PBMC will be cryopreserved for subsequent flow cytometry of cell populations and sorting of monocytes for transcriptional analysis of genes upregulated in active cGVHD. The primary collection of blood for these analyses of baricitinib effect on cGVHD will be collected prior to dose and 2 hours after dose at the following timepoints: baseline, at the time of any increase in dose level. Each aliquot contains 10×10^6 cells—with no more than cells in a single vial. All samples collected will be cryopreserved and frozen for future analyses as detailed in Section 5.2.1.
2. **Plasma** will be assayed for BAFF, CXCL9/CXCL10, IL-6, TNF α , and other IFN-induced chemokines. Take one 1 mL aliquot of plasma from each of the CPTs, without disturbing the cell interface, and place into standard cryovials. Barcode as buffy plasma and store at -80°C. All samples collected will be cryopreserved and frozen for future analyses as detailed in Section 5.2.1.
 1. Additionally, ELISA assays may include but not be limited to the following proposed biomarkers of cGVHD: CXCL9, MMP3, DKK3, ST2, CD163
 2. Additional or alternative plasma factors will be considered based upon relevant cGVHD biomarkers identified by the end of biospecimen accrual.
3. **Monocyte transcriptome:** Monocytes will be sorted from PBMC for Nanostring evaluation of the monocyte transcriptome. This would be done on cryopreserved cells at the end of the study. Monocytes circulate throughout the body, are responsive to a variety of cytokines in tissues affected by cGVHD and may therefore serve as a reporter for changes in cGVHD-affected tissues.
4. **Lymphocyte populations.** Assays characterizing lymphocyte populations will be performed to include, but not be limited to, assessments of %CXCR3+ T-cells, %T-reg cells and %CD21 B-cells. Furthermore, multilineage lymphocyte immune reconstitution after transplant will be investigated to examine the impact of JAK1/2 inhibition on lymphopoiesis (CD3, CD4, CD8, B and NK populations). At baseline prior to dose, 2 weeks, 12 weeks, 24 weeks, 36 weeks, and 48 weeks and if PI deems necessary at end of treatment and followup visits, one 3mL lavender (EDTA) tube will be drawn and lymphophenotyping will be performed using Clinical Center's CLIA certified Immunophenotyping panel and reported in the CRIS. Further research assessments of the percentages of regulatory T cells, of naïve, memory and effector T cells and of B cell transitional, naïve and memory populations will be done in the Blood Processing Core ([name]). Active cGVHD has been associated with decreases in Treg populations,

reduced thymopoiesis (fewer naïve T cells) and increases in CD21- transitional B cell populations.

The assays indicated are designed to assess the alterations in skin, oral mucosa and in circulating lymphocytes and plasma that may result from baricitinib. If there is an increase in Th1 cells or a shift in Treg populations, this may be reflected in circulating T cell populations, plasma cytokines and tissue infiltrates.

5.1.3 Measurement of Baricitinib Serum Levels

For each dose level of baricitinib administered, one plasma sample will be collected per patient for measurement of baricitinib concentration after at least 7 days of continuous treatment (on day 15 of that cycle). This testing is performed to ensure that drug concentrations do not exceed baricitinib exposures previously studied. Each time the baricitinib dose is increased or decreased an additional single sample will be collected after at least 7 days of continuous treatment on the new dose (on day 15 of that cycle). The sample will always be collected immediately before taking the next baricitinib dose. In addition, on the first day of each dose level, blood will be taken pre-dose, then at 1, 2, and 4 hours after the dose. A sample will be collected at 24 hours after the dose in up to 10 patients as feasible, but is not required on protocol. The sample at week 12 is not collected if no change in dose level occurred. In the event of a serious adverse event or at the end of study, an additional sample may be collected within 2 hours of the last dose at the discretion of the investigator. A 3-mL blood sample will be collected immediately before taking the daily baricitinib dose. Actual dosing dates and times will be recorded. These sample collections will occur at the protocol scheduled evaluation visits at the NIH Clinical Center. Every effort will be made to collect samples as prescribed in the timeline. Samples that are collected \pm 15 minutes of collection time will not be considered a protocol deviation.

In the event of a serious adverse event (SAE) or at the end of the study, an additional sample may be collected within 24 hours of the last dose, at the discretion of the investigator. If this sample is collected, it will be as soon as possible after identification of the event and the time of the last dose and the time of sample collection will be recorded.

All samples for measurement of baricitinib will be collected, processed, stored, documented and the Blood Processing Core ([name]). Plasma samples will be batch tested for baricitinib concentration not more than two years after collection using a validated liquid chromatography with tandem mass spectrometry method, with a limit of quantification of 0.5 ng/mL, by the Clinical Pharmacology Program of the NCI, directed by [name].

